5.8.3. Adverse Events of Special Interest

Adverse events of special interest (AESI) include adjudicated arthropathies, AEs confirmed as SNS dysfunction as well as peripheral neurosensory events and joint replacements meeting pre-specified AESI criteria. AESIs will be flagged in the database using predefined tick boxes to denote the events.

Summaries of AESI incidence by treatment group will include:

- Incidence of adjudicated arthropathy events
- Incidence of adjudicated arthropathies that meet destructive arthropathy criteria
- Incidence of joint replacements AESI events
- Incidence of sympathetic nervous system dysfunction AESI events
- Incidence of peripheral neurosensory AESI events

5.8.4. Clinical Laboratory Measurements

Baseline clinical laboratory analytes and change from baseline in clinical laboratory analytes to each scheduled assessment time will be summarized with descriptive statistics for each treatment group.

Listings will be provided with flags indicating the out of laboratory range values.

A Treatment-Emergent PCSV is a laboratory value that was normal or abnormal but not meeting PCSV criteria at Screening and Baseline but became abnormal and met PCSV criteria after treatment with study drug. Definition of PCSV is listed in [Appendix 10.2](#). Treatment-Emergent PCSVs will be summarized by treatment group.

For hs-CRP and alkaline phosphatase, plots of means and medians of the observed values and change from baseline over time will be presented by treatment group.

For hs-CRP and alkaline phosphatase, subgroup analysis will be performed for the following:

- Adjudicated Arthropathy category 1 (patients without / with AA)
- Adjudicated Arthropathy category 2 (patients without AA, patients with RPOA-1, and patients with non-RPOA-1 AA)
- Destructive Arthropathy category (patients without AA, patients with non-DA AA, patients with DA)

The above laboratory summaries will be constructed for the On-Treatment Periods. Lab data collected during the Pre-Treatment and Post-Treatment Periods will be displayed in listings.

5.8.5. Analysis of Vital Signs

Vital signs (temperature, blood pressure, and respiration rate) will be summarized by baseline and change from baseline to each scheduled assessment time with descriptive statistics.

A treatment-emergent PCSV is a vital sign value that was normal or abnormal but not meeting PCSV criteria at Screening and Baseline but became abnormal and met PCSV criteria after treatment with study drug. Definitions of PCSV is listed in Section [10.3](#). Treatment-Emergent PCSVs will be summarized by treatment group.

The incidence of confirmed measurements suggesting orthostatic hypotension will also be summarized by treatment group.

The above vital sign summaries will be constructed for the On-Treatment Period. Vital sign data collected during the Pre-Treatment and Post-Treatment Periods will be displayed in listings.

5.8.6. Analysis of 12-Lead Electrocardiography

ECG parameters (ventricular rate, Heart Rate, PR interval, QRS interval, QT interval and QTc interval) will be summarized by baseline and change from baseline to each scheduled assessment time.

A treatment-emergent PCSV is an ECG value that was normal or abnormal but not meeting PCSV criteria at Screening and Baseline but became abnormal and met PCSV criteria after treatment with study drug. Definitions of PCSV is listed in Section [10.3](#). Treatment-Emergent PCSVs will be summarized by treatment group.

ECG status (i.e. normal, abnormal not clinical significant or abnormal clinical significant) will be reported. Shift tables will be provided to present the post-baseline status according to the baseline status (normal or missing/abnormal) by treatment group.

5.8.7. Physical and Neurological Examinations

The percentage of patients with new-onset clinically significant abnormal physical examinations will be summarized by treatment group showing frequency and percentage by body system for each period as well as at the end of the period. Similarly summaries will be presented for neurological exam findings. These summaries will be constructed for the on-treatment period, post-treatment period and overall during the study.

5.8.8. Joint Pain Questionnaire

The percentage of patients with worse joint pain will be summarized by visit and joint.

5.8.9. Analysis of Other Safety Variables

Other safety data includes the survey of Autonomic Symptoms, cases of AA and joint replacements.

Adjudicated Arthropathy

Adjudicated arthropathy events based on imaging data overall and by subtype will be summarized by treatment group based on the SAF. Incidence of AA (as confirmed by an independent adjudication committee) through week 36 will be summarized by treatment group based on the SAF. Time to first AA event will be summarized by Kaplan-Meier method if enough number of events occur. Cox regression model will be used for descriptively comparing each treatment group to placebo by obtaining hazard ratio estimates along with 95% confidence intervals. Swimmer plots depicting the length of the observation window per patient and indicating timepoints at which the initial event occurred, worsened and/or changed subtype category may be presented by treatment group.

Incidence of DA (as confirmed by an independent adjudication committee) through week 36 will be summarized by treatment group based on the SAF. Time to first DA event will be summarized by Kaplan-Meier method if enough number of events occur. Cox regression model

will be used for descriptively comparing each treatment group to placebo by obtaining hazard ratio estimates along with 95% confidence intervals.

All-cause joint replacements of any joint will be summarized by treatment group. The number of replacements in joints that were positively adjudicated will be summarized by treatment group. Joint replacements will also be summarized by KL score of the affected joint at screening.

In the time to event analyses, Time to first event will be calculated as: (Date of the first event – Date of the first dose of study drug +1). Patients without an event will be censored at the last visit for AA and DA in the analysis.

Survey of Autonomic Symptoms

The number of patients reporting the presence of each symptom/health problem assessed will be presented by treatment group at each scheduled visit. The number of symptoms reported and total symptom impact score will be presented by treatment group at each scheduled visit.

All-cause Joint Replacements

The number and percentage of patients with all-cause joint replacements will be presented by treatment group On-Treatment and Post-Treatment Periods based on the SAFs. The number of replacements in joints that were positively adjudicated will be summarized by treatment group. Joint replacements will also be summarized by KL score of the affected joint at screening. Additionally, the number and percentage of patients who reported joint replacements at the End of Study Phone Call will be summarized.

The time to JR is calculated as:

$$= (\text{Date of JR} - \text{Date of first dose of study drug}) + 1$$

5.9. Analysis of Pharmacokinetics and Drug Concentration Data

Summaries of concentrations of functional fasinumab will be presented by nominal time point and dose. Plots of individual concentration over time will be presented by actual day. Plots of mean or median concentration of functional fasinumab will be presented by dose and nominal day or week. No formal statistical analysis will be performed.

5.10. Analysis of Immunogenicity Data

5.10.1. Analysis of Anti-Drug Antibody Data

The immunogenicity variables described in Section [4.8](#) will be summarized using descriptive statistics. Immunogenicity will be characterized by ADA responses and titers observed in patients in the ADA analysis set. ADA response categories and titer categories are defined as follows:

ADA response categories

- ADA Negative, defined as ADA negative response at all time points, regardless of any missing samples.
- Pre-existing immunoreactivity, defined as either an ADA positive response in the ADA assay at baseline with all post first dose ADA results negative, OR a positive response at baseline with all post first dose ADA responses less than 9-fold over baseline titer levels.
- Treatment-emergent response, defined as a positive response in the ADA assay post first dose when baseline results are negative or missing. The treatment-emergent responses will be further characterized as Persistent, Indeterminate or Transient:
 - Persistent Response - Treatment-emergent ADA positive response with two or more consecutive ADA positive sampling time points, separated by at least 16-week period (based on nominal sampling time), with no ADA negative samples in between, regardless of any missing samples.
 - Indeterminate Response - Treatment-emergent ADA positive response with only the last collected sample positive in the ADA assay, regardless of any missing samples.
 - Transient Response - Treatment-emergent ADA positive response that is not considered persistent or indeterminate, regardless of any missing samples.
- Treatment-boosted response, defined as a positive response in the ADA assay post first dose that is greater than or equal to 9-fold over baseline titer levels, when baseline results are positive.

Titer categories (Maximum titer values)

- Low (titer <1,000)
- Moderate ($1,000 \leq \text{titer} \leq 10,000$)
- High (titer >10,000)

The following analysis will be provided:

- Number (n) and percent (%) of ADA-negative patients (pre-existing immunoreactivity or negative in the fasinumab ADA assay at all time points) by treatment groups
- Number (n) and percent (%) of treatment-emergent ADA positive patients by treatment groups and ADA titer categories
 - Number (n) and percent (%) of persistent treatment-emergent ADA positive patients

- Number (n) and percent (%) of indeterminate treatment-emergent ADA positive patients
Number (n) and percent (%) of transient treatment-emergent ADA positive patients
- Number (n) and percent (%) of treatment-boosted ADA positive patients by treatment groups and ADA titer categories

Listing of all ADA titer levels will be provided for patients with pre-existing, treatment-emergent and treatment-boosted ADA response.

5.10.2. Association of Immunogenicity with Exposure, Safety and Efficacy

5.10.2.1. Immunogenicity and Exposure

Potential association between immunogenicity variables and systemic exposure to fasinumab will be explored by treatment groups. Plots of fasinumab concentration may be provided for analyzing the potential impact of ADA response status and titer on PK.

5.10.2.2. Immunogenicity and Safety and Efficacy

Potential association between immunogenicity variables and safety may be explored with a primary focus on the following safety events during the TEAE period:

- Injection site reaction (serious or severe and lasting 24 hours or longer)
- Hypersensitivity (SMQ: Hypersensitivity [Narrow])
- Anaphylactic Reaction (SMQ: Anaphylactic Reaction [Narrow])

Potential association between immunogenicity variables and efficacy and safety endpoints may be explored (e.g. scatter plot or spaghetti plot). The above-mentioned safety and efficacy analyses will be conducted using the following categories:

- ADA positive patients, that is patients with treatment-emergent or treatment-boosted response.
- ADA negative patients, that is patients with pre-existing immunoreactivity or negative in the ADA assay at all time points.
- Patients with persistent treatment-emergent ADA response.
- Maximum post-baseline titer in treatment-emergent or treatment-boosted ADA positive patients:
 - Low (titer <1,000)
 - Moderate ($1,000 \leq \text{titer} \leq 10,000$)

- High (titer >10,000)

6. DATA CONVENTIONS

The following analysis conventions will be used in the statistical analysis.

For categorical variables, patients with missing data are not included in calculations of percentages unless otherwise specified. When relevant, the number of patients with missing data is presented.

6.1. Definition of Baseline for Variables

Unless otherwise specified, the baseline assessment for all measurements will be the latest available valid measurement prior to randomization.

6.2. Data Handling Conventions for Efficacy Data

Missing data items for questionnaires

Rules for handling missing data for efficacy assessments due to missing individual item data will follow each questionnaire's instrument manual. WOMAC scores will be computed when one pain item, one stiffness item, or at most 3 physical function items are missing. The missing items will be imputed by the mean of available items within the same subscale. The scores will be set to missing if more items are missing.

Due to public health measures implemented to address the world-wide COVID-19 pandemic, some sites may suspend onsite study visits or patients may opt not to attend. To mitigate data loss, patients may be contacted via telephone and the results of their efficacy measures transcribed verbally and entered into the eCOA devices. For analysis purposes, this data will be treated the same as efficacy data collected in an onsite visit and will be utilized in the efficacy analyses. Since all patients already had chance to complete week 16 visit prior to COVID-19 pandemic, there is no impact to the main efficacy endpoints and primary safety endpoints at week 16.

Data collected through the implementation of new CRFs regarding the impact of the COVID-19 pandemic (e.g. discontinuation due to COVID-19) on the patients will be summarized including missing visits, doses, and reason.

6.3. Data Handling Convention for Repeat Data

Orthostatic Hypotension data

This applies specifically to the data handling of repeat measurements in the assessment of orthostatic hypotension. Per protocol, if the initial vital assessment for orthostatic hypotension is consistent with the definition of orthostatic hypotension, the supine, standing blood pressure or pulse should be repeated up to 2 more times. The guideline for the repeat assessments are shown below:

Initial Assessment	Repeat Assessment 1	Repeat Assessment 2	Does patient meet OH criteria	Value to be used in the analysis
Does not meet OH definition	N/A	N/A	No	Initial Assessment
Meets OH definition - repeat	Does not meet definition - repeat	Does not meet definition	No	N/A
Meets OH definition - repeat	Does not meet definition - repeat	Meets OH definition	Yes, AE of OH reported	Repeat Assessment 2
Meets OH definition - repeat	Meets OH definition	N/A	Yes, AE of OH reported	Repeat Assessment 1

Baseline for the assessment of orthostatic hypotension vital assessments uses the last available assessment prior to the start of study drug. Measurements post-baseline will not be averaged. Rather frequency counts for patients meeting OH criteria for orthostatic hypotension will reflect the scenario as shown on the table.

Patient reported outcomes data

Should there be duplicate entries for patient reported outcomes data (not including diary data), the average of the entries will be used for questionnaires with numerical values such as the WOMAC. The worst category will be used in the analysis for questionnaires with categorical responses such as the SAS and Joint Pain Questionnaire.

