8.2.4. Safety Procedures

8.2.4.1. Vital Signs

Vital signs, including body temperature and respiratory rate, will be collected pre-dose at time points according to Table 1. Blood pressure and heart rate will be collected as part of the orthostatic hypotension assessments. If at any visit after the randomization visit the pulse is less than 45 bpm, an ECG with rhythm strip will be obtained to confirm the heart rate and rhythm.

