4.6.7. Orthostatic Hypotension

A patient will be determined to have orthostatic hypotension if any of the following criteria are met:

- If the supine blood pressure is <160 mmHg systolic, a decrease in either the 1 or 3 minute standing systolic blood pressure of ≥ 20 mmHg or a decrease in the standing diastolic blood pressure of ≥ 10 mmHg from the supine systolic or diastolic blood pressure

OR

- If the supine blood pressure is ≥ 160 mmHg systolic, a decrease in either the 1 or 3 minute standing systolic blood pressure of ≥ 30 mmHg or a decrease in the standing diastolic blood pressure of ≥ 15 mmHg from the supine systolic or diastolic blood pressure

OR

- An increase in either the 1 or 3 minute standing heart rate of ≥ 30 bpm from the supine heart rate

OR

- The patient is unable to stand for either one of the standing blood pressure measurements due to dizziness or lightheadedness

Confirmed orthostatic hypotension is defined as initial assessment meeting the above orthostatic hypotension criteria confirmed by subsequent repeated assessments per protocol.

4.6.8. 12-Lead Electrocardiography

A standard 12-lead ECG will be performed according to the Schedule of Events in [Appendix 10.1](#). Heart rate will be recorded from the ventricular rate, and the PR, QRS, and QT, QTc intervals, and ECG status (normal, abnormal not clinically significant or abnormal clinical significant) will also be recorded.

QTcF and QTcB are defined as follows:

$$QTcF (ms) = QT/RR^{1/3} \text{ and } QTcB (ms) = QT/RR^{1/2},$$

where QT is the uncorrected QT interval measured in ms, and RR is 60/HR with HR being the heart rate in beats per minute.

PCSV ranges will be applied to the ECG parameter values as applicable (see [Appendix 10.2](#) for PCSV definitions).

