Hematocrit	
≤ 0.37 v/v and > 0.37 v/v at baseline for Male; ≤ 0.32 v/v and > 0.32 v/v at baseline for Female ≥ 0.55 v/v and < 0.55 v/v at baseline for Male; ≥ 0.5 v/v and < 0.5 v/v at baseline for Female
	Two Criteria are independent
RBC	
Female < 3 Tera/L and baseline ≥ 3 Tera/L ≥ 6 Tera/L and baseline < 6 Tera/L
 
Male < 4 Tera/L and baseline ≥ 4 Tera/L ≥ 7 Tera/L and baseline < 7 Tera/L
	
Unless specifically required for particular drug development, the analysis is redundant with that of Hb.
 
Otherwise, consider FDA criteria.

Parameter	Treatment Emergent PCSV	Comments
Platelets	<100 Giga/L and \geq 100 Giga/L at baseline	International Consensus meeting on drug-induced blood cytopenias, 1991. Two independent criteria
	\geq 700 Giga/L and < 700 Giga/L at baseline	
Urinalysis		
pH	\leq 4.6 and > 4.6 at baseline	Two independent criteria
	\geq 8 and < 8 at baseline	
Vital signs		
HR	\leq 50 bpm and decrease from baseline \geq 20 bpm	To be applied for all positions (including missing) except STANDING.
	\geq 120 bpm and increase from baseline \geq 20 bpm	
SBP	\leq 95 mmHg and decrease from baseline \geq 20mmHg	To be applied for all positions (including missing) except STANDING.
	\geq 160 mmHg and increase from baseline \geq 20 mmHg	
DBP	\leq 45 mmHg and decrease from baseline \geq 10 mmHg	To be applied for all positions (including missing) except STANDING.
	\geq 110 mmHg and increase from baseline \geq 10 mmHg	

Parameter	Treatment Emergent PCSV	Comments
Orthostatic Hypotension	Su SBP < 160 mmHg -	
	SBP St – Su ≤ - 20 mmHg	
	DBP St – Su ≤ - 10 mmHg	
	Su SBP ≥ 160 mmHg -	
	SBP St – Su ≤ - 30 mmHg	
	DBP St – Su ≤ - 15 mmHg	
Weight	≥5% increase from baseline	FDA Feb 2007.
	≥5% decrease from baseline	
ECG		Ref.: CPMP 1997 guideline. ICH E14 2005
HR	≤50 bpm and decrease from baseline ≥20 bpm	
	≥120 bpm and increase from baseline ≥20 bpm	
PR	≥220 ms and increase from baseline ≥20 ms	
QRS	≥120 ms & < 120 ms at baseline	

Parameter	Treatment Emergent PCSV	Comments
QTc	Absolute values (ms) >450 ms and baseline <=450 ms >480 ms and baseline <=480 ms >500 ms and <= 500 ms at baseline Increase from baseline Increase from baseline 30-60 ms Increase from baseline >60 ms	To be applied to any kind of QT correction formula. $\Delta QTc > 60$ ms are the PCSA to be identified in individual subjects/patients listings.

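### SAP 6.3 gives no analysis value to a visit with an unconfirmed first orthostatic finding, and the orthostatic PCSV row in Table 3 omits two of the four criteria in SAP 4.6.7

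*SAP*

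**What the plan says.** **Repeat readings.** The table in SAP 6.3 has four rows and a column naming the value to analyse. Where the first assessment meets the OH definition and neither repeat does, the row is "Meets OH definition - repeat Does not meet definition - repeat Does not meet definition No N/A". SAP 6.3 adds that post-baseline readings are not averaged: "Rather frequency counts for patients meeting OH criteria for orthostatic hypotension will reflect the scenario as shown on the table".

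**Where blood pressure comes from and how it is used.** Protocol 8.2.4.1 states: "Blood pressure and heart rate will be collected as part of the orthostatic hypotension assessments". SAP 5.8.5 states: "Vital signs (temperature, blood pressure, and respiration rate) will be summarized by baseline and change from baseline", at each scheduled assessment. SAP 6.4 allows no imputation of missing vital signs.

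**Definition and PCSV row.** SAP 4.6.7 (and Protocol 8.2.3.4) counts a patient as having OH if any of four criteria is met. Two are blood-pressure drops, one for each supine systolic range. The third is "An increase in either the 1 or 3 minute standing heart rate of ≥ 30 bpm from the supine heart rate". The fourth is "The patient is unable to stand for either one of the standing blood pressure measurements due to dizziness or lightheadedness". The OH row of SAP 10.2, Table 3 holds only blood-pressure differences, for example "SBP St – Su ≤ - 20 mmHg" when "Su SBP < 160 mmHg".

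**The concern.** Two rows of the SAP 6.3 table end in the same classification, not OH, but are treated differently. One keeps its reading and the other gets none. The only thing that separates them is an abnormal first reading, so whether a visit contributes a blood pressure depends on the outcome being monitored. Outcome-dependent missingness should not be written into a safety summary, least of all for a drug class where sympathetic effects are the stated reason for the monitoring.

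The PCSV row raises a different problem. The SAP defines OH one way in 4.6.7 and screens for it a narrower way in Table 3. A patient who qualifies only by heart rate, or only by being unable to stand, is OH in one table and not flagged in the other, and the SAP does not explain the difference.

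At stake is the completeness and consistency of two descriptive safety displays. No primary or secondary endpoint is involved.

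**Working it through.** The documents state no figure for OH, so there is none to reproduce. The check compares the rules and then sizes the gap under assumptions.

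**Step 1: the four rows of SAP 6.3.**

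| Initial | Repeat 1 | Repeat 2 | OH? | Value analysed | Last assessment done |
|---|---|---|---|---|---|
| No | not done | not done | No | Initial | Initial |
| Yes | No | No | No | **none** | Repeat 2 |
| Yes | No | Yes | Yes | Repeat 2 | Repeat 2 |
| Yes | Yes | not done | Yes | Repeat 1 | Repeat 1 |

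Three of the four rows use the last assessment done. SAP 6.3 also takes the last available pre-drug assessment as the OH baseline. Only the second row departs from this.

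**Step 2: can another rule supply the value?**
- SAP 6.5 picks the measurement closest to the target day and breaks ties by study day, so it cannot choose among repeats on the same day.
- The first-observation rule in SAP 6.7 covers laboratory values only.
- SAP 6.4 rules out imputation.

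The visit therefore has no designated blood pressure for SAP 5.8.5.

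**Step 3: does the missing value carry into the PCSV analysis?** SAP 5.8 puts all post-baseline data, scheduled and unscheduled, into that analysis, and SAP 6.5 says much the same. SAP 6.3 does not say whether its table overrides them. The point is unresolved.

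**Step 4: size of the gap (assumed rates; about 90 patients per arm is the planned size).** Let p be the chance that one assessment meets the definition, independently of the others. The probability of the no-value path is p(1 − p)².

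| p | p(1 − p)² | × 90 |
|---|---|---|
| 2% | 0.0192 | 1.7 |
| 5% | 0.0451 | 4.1 |
| 10% | 0.0810 | 7.3 |
| 20% | 0.1280 | 11.5 |

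Repeats on the same patient are likely to agree with the first reading. If each repeat is positive with probability r after a positive first reading, the share of first positives left without a value is (1 − r)²: 49% for r = 0.3, 25% for r = 0.5 and 9% for r = 0.7. For example, with p = 5% and r = 0.5 the count is 90 × 0.05 × 0.25 = 1.1 patients per arm per visit.

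**Step 5: PCSV row against the definition.**

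| SAP 4.6.7 criterion | In Table 3 OH row? |
|---|---|
| Drop, supine systolic below 160 mm Hg | Yes |
| Drop, supine systolic 160 mm Hg or above | Yes |
| Standing heart-rate rise of at least 30 bpm | No |
| Unable to stand for either reading | No |

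Two of four are absent. No other vital-sign row picks them up, because the HR, SBP and DBP rows in Table 3 exclude the standing position.

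**The case against.** A reader might infer that the sympathetic-safety measures lose the very patients they should show. The documents do not support that.
- An unconfirmed finding counted as not OH follows the SAP's own definition of confirmed OH (4.6.7).
- Confirmed-OH incidence uses all four criteria and is tabulated by arm separately from the PCSVs (5.8.5).
- Adverse event reporting and specialist-diagnosed sympathetic dysfunction (4.6.2) use neither the 6.3 value nor the PCSV row.

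A reader might also infer that the gap makes fasinumab look more normal. That is not shown. Repeat Assessment 2 in that row does not meet the OH definition, so compared with using it, the rule omits a reading below the OH threshold. Compared with using the initial reading, it omits one that met the definition. The direction depends on the comparison, and nothing shows a difference between arms.

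Nor does inability to stand always mean there is no standing pressure. The criterion covers either measurement, so a patient may have a 1-minute reading and fail at 3 minutes.

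It is also fair to say that SAP 6.3 is introduced as a rule for the OH assessment and its frequency counts, that SAP 5.8.5 does not cite it, that pulse is not in the SAP 5.8.5 list (so the by-visit loss is clear only for blood pressure), and that SAP 10.2 calls its criteria a reference to be settled before lock.

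These points narrow the consequences but do not remove the defects. The SAP 6.3 column names an analysis value, no other rule supplies one, and the SAP contains no other PCSV list.

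**Conclusion.** The point holds as a minor correction to the safety summaries. Followed literally, SAP 6.3 leaves a visit with an unconfirmed first OH finding without a blood pressure for SAP 5.8.5, and this happens because the first reading was abnormal. Whether the gap extends to the PCSV analysis is unclear, because SAP 5.8 points the other way. The number affected is unknown. The independence assumption gives about 2 to 12 of 90 per arm per visit for p from 2% to 20%, and agreement between repeats lowers it. The size and direction of any bias are unknown.

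The PCSV finding needs no assumption: two of the four criteria in SAP 4.6.7 cannot trigger the OH row of Table 3. Neither defect changes the confirmed-OH count or any primary or secondary endpoint.

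**What to change.** 1. In the SAP 6.3 table, replace N/A in the second row with Repeat Assessment 2 for by-visit summaries, and keep the OH classification as No. This is the last assessment done, as in the other three rows.
2. State in SAP 6.3 that all readings, including the initial one, still enter the PCSV analysis under SAP 5.8.
3. While editing, add a row for a positive initial assessment, a negative first repeat and no second repeat. The protocol allows up to two repeats, so this path can occur.
4. In Table 3, add the standing heart-rate rise of at least 30 bpm and inability to stand to the OH row, so that it matches SAP 4.6.7. Note beside it that PCSV and confirmed-OH counts will still differ, because only the latter requires confirmation on repeat.

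The cost is a few table edits in the SAP, made before unblinding. No new data are needed, since confirmed OH already requires the same items, and no protocol amendment is needed.
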